## 2) Objectives

The purpose of the study is to investigate the effects of aromatherapy on pain, anxiety, and nausea in patients on an acute care unit. The primary objective of this project is to determine whether Elequil aromatherapy tabs show a measurable benefit in reducing patient reported pain, anxiety, and nausea, thus reducing the use of anxiolytic, antiemetic, or opioid medications. The secondary objective is to identify the effectiveness of aromatherapy on improved sleep and improved patient satisfaction and well-being.

Aromatherapy has been studied and shown effective for the decreased effects of pain, anxiety, and nausea. We are hypothesizing that the use of aromatherapy has a positive effect in decreasing patient-reported pain, anxiety, and nausea, and increasing sleep and overall patient satisfaction.

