## 3) Background

People are hospitalized every day, with many of them experiencing ailments such as pain, nausea, and anxiety, on top of the symptoms that are related to their admitting diagnoses. As nurses, the primary responsibilities are to function as a caregiver to help manage physical conditions, treat illness, and educate to prevent further worsening of health conditions. Assessing, managing, and treating uncomfortable symptoms is an integral part of nursing care. Interventions for these primarily include pharmaceutical interventions. The use of aromatherapy is an alternative treatment that can be used in addition to medications. Clinical aromatherapy is the controlled and therapeutic use of essential oils in the clinical setting for specific, measurable outcomes and is a natural therapy increasingly being used to improve symptoms and maintain health and well-being during a hospital stay.

The encouragement of alternative, non-pharmaceutical means to decrease symptoms is not a wide-spread practice. Hospitals do not necessarily see the use of essential oils as an effective means to decrease somatic complaints. This study will try to expand upon the limited literature and studies regarding the use of aromatherapy and its effectiveness in decreasing the presence of pain, nausea, and anxiety in the hospital setting.

There is limited evidence that shows that the use of aromatherapy is effective

---

 Buckle, J. The role of aromatherapy in nursing care. *Nurs Clin North Am.* 2001;36(1):57-72.

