## PROTOCOL TITLE: Aromatherapy on Tower 4 (Non-Otolaryngology)

in decreasing somatic complaints. One study concluded that essential oils generally resulted in significant clinical improvements based on their intended use. Cho found that aromatherapy use resulted in reduced anxiety, increased sleep, and stabilized blood pressure. Moeini and colleagues demonstrated that the use of aromatherapy significantly improved the quality of sleep with the use of essential oils. While the majority of aromatherapy studies were done in the intensive care unit (ICU) setting, or outpatient setting, all concluded that further studies needed to be done. In an effort to provide non-pharmacologic adjunctive treatments for symptom management, aromatherapy has been explored in the inpatient setting.

We will be using Elequil aromatabs® to determine the effectiveness of aromatherapy in the hospital setting. The following scents, their common uses and estimated aromatab® duration of use are:

- Lavendar: Promotes relaxation, comfort, and sleep. Lasts 8 hours.
- Lavendar-Sandalwood: Promotes relaxation, comfort, and sleep. Lasts 8 hours or more.
- Lavendar-peppermint: Promotes relaxation during pain, calm anxiousness, and soothe queasiness. Lasts 8 hours.
- Orange-Peppermint: Uplifts, energizes, and soothes queasiness. Lasts 8 hours.

The chosen essential oils will be inhaled by the patient when the aromatherapy tab is opened and affixed to their hospital gown.

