### Inclusion criteria:

- Age 18 years or older
- Admission to Tower 4 for an anticipated inpatient stay >24 hours
- Alert and oriented
- Capable of using a visual scale to self-report symptoms
- Naïve to the use of aromatherapy for the use of decreasing pain, anxiety, and/or nausea to participate.
- Not on a pediatric service

The specific criteria for subject selection are patients admitted to Tower 4, an acute care/telemetry unit, who are conscious and able to communicate, that understands the purpose of the study and is competent and can give consent. The patient must not include any of the following:

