### 5) Study Timelines

Participants of the study will ideally wear the aromatherapy tab on their gown for at least 8 hours to assess its effectiveness. After a minimum of 8 hours has elapsed, they will be given a follow up assessment tool to evaluate their symptoms and their experience in using aromatherapy.

- Identification of eligibility
- Consent
- Assessment 1 (Hour 0)  
Awake - complete assessment tool.
- Aromatherapy tab application
- Assessment 2 (Hour 8)  
Sleeping - no assessment/document sleep  
Awake – complete end assessment tool.  
Satisfaction assessment

If patient prefers, they can continue to utilize aromatherapy, otherwise tab is to be removed, and study is complete.

- Assessment 3 (Hour 12-24)
- Aromatherapy tab removal (after the maximum 24 hours worn)
- Additional data collection as noted below (medication use)

Individual subject participation will total up to 8 hours to a maximum of twenty-four hours.

We anticipate that our goal enrollment of one hundred subjects will be accomplished within six months (from first subject enrolled to last subject). Our total estimate for study completion is twelve months.

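### The objective, hypothesis and endpoints claim that the tab is effective and so lowers medication use, but one unblinded group with no concurrent comparator cannot support either claim

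*Protocol*

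**What the plan says.** Protocol section 2) Objectives sets the primary objective as to "determine whether Elequil aromatherapy tabs show a measurable benefit in reducing patient reported pain, anxiety, and nausea, thus reducing the use of" anxiolytics, antiemetics or opioids. The hypothesis is that "the use of aromatherapy has a positive effect in decreasing patient-reported pain, anxiety, and nausea", and it goes on to expect "increasing sleep and overall patient satisfaction". On the other outcomes the section says: "The secondary objective is to identify the effectiveness of aromatherapy on improved sleep and improved patient satisfaction and well-being".

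Section 6) Study Endpoints keeps the same claim. The lead-in to the primary list asserts that tab use is effective on the pain, anxiety and nausea scores. The lead-in to the secondary list asserts effectiveness in decreasing a list that opens with the three medication totals and also contains sleep, satisfaction and well-being. Section 3) Background says the tabs are used "to determine the effectiveness of aromatherapy in the hospital setting".

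The design is set out in sections 5) Study Timelines, 7) Procedures Involved and 18) Drugs or Devices. After consent and a baseline rating, the subject names a priority symptom, is offered the matching tab and chooses the scent strength. Ratings follow at Hour 8 and, for those who carry on, at Hour 12-24. The tab supplements the subject's medication plan. Medication use is taken from the chart. The enrollment goal is 100 subjects, with no division into groups.

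**The concern.** The aim is causal: the tab lowers symptoms and, through that, lowers drug use. A causal statement needs some view of what would have happened over the same hours without the tab, and the described design has none. A fall in scores would satisfy the protocol's own wording of effectiveness whatever produced it, and the medication totals could be read as a medication-sparing result.

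The study team plans to present and publish the findings (section 7, Reporting/dissemination). The wording of the objective and endpoints therefore sets what will be claimed. Analysis windows, tests and handling of missing ratings can properly be left to a statistical analysis plan. A comparator cannot, because no analysis can add patients who were never enrolled.

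**Working it through.** **1. Claim against design.** The protocol uses neither the term single-arm nor the term unblinded; both follow from its procedures.

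| Element | What the protocol gives |
|---|---|
| Allocation | Tab matched to the subject's priority symptom; no randomisation |
| Comparator | None: no untreated group, unscented tab or historical reference |
| Blinding | None: the subject chooses the scent strength |
| Other treatment | Usual medication continues |
| Contrast available | Each subject's rating before and after |

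The observed mean change is the tab effect plus everything else that moves scores between ratings: natural course, concurrent drugs, expectation and regression to the mean. The design yields only the sum.

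**2. Medication use.** Totals come from the chart and the protocol states no pre-tab window. A statistical analysis plan could define one. The result would still be an uncontrolled before-and-after figure, open to the ordinary change in drug needs during an admission. The word linking less symptom burden to less drug use in the objective would stay untestable.

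**3. Secondary outcomes.** Satisfaction is asked only at follow-up, so it has no baseline. Sleep and well-being have no comparator either.

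**4. Illustration of size.** The protocol gives no alpha, power, effect size or SD for its goal of 100, so there is no figure to reproduce. Inputs: n = 100 is the enrollment goal. Assumed, not in the documents: one endpoint, a paired two-sided 5% t-test, a true tab effect of zero, and a background improvement of d SDs of the change score.

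Probability of a significant benefit = P(T > t at 0.975 with n − 1 df), where T is noncentral t with noncentrality d√n and √100 = 10.

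| d | d√n | P(significant benefit) | On a 0-10 pain scale, if SD of change is 2 to 3 points (assumed) |
|---|---|---|---|
| 0 | 0 | 0.025 | 0 |
| 0.1 | 1 | 0.166 | 0.2 to 0.3 points |
| 0.2 | 2 | 0.508 | 0.4 to 0.6 points |
| 0.3 | 3 | 0.844 | 0.6 to 0.9 points |

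A normal approximation to the two-sided rejection probability, Φ(d√n − 1.96) + Φ(−d√n − 1.96), gives 0.170, 0.516 and 0.851 for d = 0.1, 0.2 and 0.3, in agreement.

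Regression to the mean alone could be of this order. Suppose baseline ratings lie k SDs above the subjects' usual level, with test-retest correlation r. The expected fall in SDs of change is k(1 − r)/√(2(1 − r)). With k = 0.5 and r = 0.7 this is 0.15/√0.6 = 0.19; with k = 1.0 and r = 0.5 it is 0.50/1.00 = 0.50. Both k and r are assumptions.

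**The case against.** The strongest reply is that this is a small, minimal-risk nursing study whose protocol also uses softer language, such as investigating effects. It commits to no particular test, it refers the analysis to a statistician, and the proposed edit leaves attribution just as impossible as before. Careful reporting could prevent an over-claim. It can also be said that the percentages above show only that 100 paired ratings will detect almost any mean shift.

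The last remark is right, and the figures are offered only as illustration. The rest does not remove the problem. The causal wording stands in the primary objective, the hypothesis and the endpoint definitions, so a faithful report of the protocol would itself be the over-claim.

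Some stronger readings are tempting but not supported:

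- A reader might infer that the trial will probably give a false positive. The documents give no background drift, and worsening could equally hide a real effect. The entry criterion "Capable of using a visual scale to self-report symptoms" is about the ability to give ratings; the criteria set no symptom threshold, so neither direction can be presumed.
- A reader might infer that every subject wears a tab. It is offered, and section 10) Withdrawal of Subjects provides for opting out before use. The one-group reading does not depend on this.
- A reader might infer that Hour 8 has to be the sole primary time. Sections 5 and 7 allow assessment from 8 to 24 hours, and a missing comparator does not settle that choice.
- A reader might want every mention of effectiveness removed. The Background phrase "its effectiveness in decreasing the presence of pain, nausea, and anxiety in the hospital setting" describes the literature that the study hopes to extend, and the timeline's "for at least 8 hours to assess its effectiveness" is incidental. Neither defines what the trial concludes.
- Placing sleep and satisfaction under a heading about decreases, when section 2 expects increases, is a slip of direction. It is a separate matter and adds no weight here.

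**Conclusion.** The concern holds. The primary objective, hypothesis and endpoints assert that the tab causes benefit and, through it, lower medication use, and the described design cannot show either. This rests on the protocol's own text and needs no numerical assumption: any non-zero background change is counted as tab effect.

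The possible size depends wholly on assumed inputs. For an inert tab under the test and sample size assumed above, the chance of a significant benefit rises from 2.5% with no background change to about 17%, 51% or 84% with an improvement of 0.1, 0.2 or 0.3 SD of change. These are not estimates for this trial.

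Nothing here shows that the tab does not work or that a one-group study is unacceptable. The fault is that the stated conclusion exceeds what the design can deliver.

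**What to change.** Change the wording and leave the design as it is.

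1. Restate the primary objective, hypothesis and primary endpoints as change from baseline in pain, anxiety and nausea scores among patients wearing a tab in addition to usual medication. Leave the primary follow-up time to the sponsor or the statistical analysis plan.
2. In section 2, delete the clause beginning with thus. In section 6, delete the effectiveness wording from the lead-in to both endpoint lists.
3. Report medication use, including any pre-tab comparison that a statistical analysis plan defines, descriptively. Do the same for sleep, satisfaction and well-being, and reword the secondary objective to match. This also removes the conflict of direction between sections 2 and 6.
4. Align the sentence in section 3 that says why the tabs are used (determining effectiveness), and state that no effectiveness or medication-sparing conclusion will be drawn from the uncontrolled comparison.

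This needs no extra patients, tabs, visits or data. The cost is a more modest claim. Keeping the effectiveness question would need a concurrent comparator, which is not requested here. For scale only, and again assuming a two-sided 5% level, the same 100 subjects split 50/50 would have 80% power for a standardised difference of 0.56 and 32% for 0.3.

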## 3) Background

People are hospitalized every day, with many of them experiencing ailments such as pain, nausea, and anxiety, on top of the symptoms that are related to their admitting diagnoses. As nurses, the primary responsibilities are to function as a caregiver to help manage physical conditions, treat illness, and educate to prevent further worsening of health conditions. Assessing, managing, and treating uncomfortable symptoms is an integral part of nursing care. Interventions for these primarily include pharmaceutical interventions. The use of aromatherapy is an alternative treatment that can be used in addition to medications. Clinical aromatherapy is the controlled and therapeutic use of essential oils in the clinical setting for specific, measurable outcomes and is a natural therapy increasingly being used to improve symptoms and maintain health and well-being during a hospital stay.

The encouragement of alternative, non-pharmaceutical means to decrease symptoms is not a wide-spread practice. Hospitals do not necessarily see the use of essential oils as an effective means to decrease somatic complaints. This study will try to expand upon the limited literature and studies regarding the use of aromatherapy and its effectiveness in decreasing the presence of pain, nausea, and anxiety in the hospital setting.

There is limited evidence that shows that the use of aromatherapy is effective

---

 Buckle, J. The role of aromatherapy in nursing care. *Nurs Clin North Am.* 2001;36(1):57-72.

## PROTOCOL TITLE: Aromatherapy on Tower 4 (Non-Otolaryngology)

in decreasing somatic complaints. One study concluded that essential oils generally resulted in significant clinical improvements based on their intended use. Cho found that aromatherapy use resulted in reduced anxiety, increased sleep, and stabilized blood pressure. Moeini and colleagues demonstrated that the use of aromatherapy significantly improved the quality of sleep with the use of essential oils. While the majority of aromatherapy studies were done in the intensive care unit (ICU) setting, or outpatient setting, all concluded that further studies needed to be done. In an effort to provide non-pharmacologic adjunctive treatments for symptom management, aromatherapy has been explored in the inpatient setting.

We will be using Elequil aromatabs® to determine the effectiveness of aromatherapy in the hospital setting. The following scents, their common uses and estimated aromatab® duration of use are:

- Lavendar: Promotes relaxation, comfort, and sleep. Lasts 8 hours.
- Lavendar-Sandalwood: Promotes relaxation, comfort, and sleep. Lasts 8 hours or more.
- Lavendar-peppermint: Promotes relaxation during pain, calm anxiousness, and soothe queasiness. Lasts 8 hours.
- Orange-Peppermint: Uplifts, energizes, and soothes queasiness. Lasts 8 hours.

The chosen essential oils will be inhaled by the patient when the aromatherapy tab is opened and affixed to their hospital gown.

### 4) Inclusion and Exclusion Criteria

Setting:

Upon admission to Tower 4- an acute care, remotely monitored telemetry unit at UC Davis Medical Center in Sacramento, CA., if the patient is interested in participating in the study, the patient will first be evaluated on whether they meet

---

 Johnson, Rivard, Griffin Kolste, Joswiak, Kinney, Dusek. The effectiveness of nurse-delivered aromatherapy in an acute care setting. *Complementary Therapies in Medicine*. 2016; 25: 164-169.

 Elequil Aromatab Informational handout. <https://www.beekley.com/>

## PROTOCOL TITLE: Aromatherapy on Tower 4 (Non-Otolaryngology)

the inclusion criteria to participate in the study.

### Inclusion criteria:

- Age 18 years or older
- Admission to Tower 4 for an anticipated inpatient stay >24 hours
- Alert and oriented
- Capable of using a visual scale to self-report symptoms
- Naïve to the use of aromatherapy for the use of decreasing pain, anxiety, and/or nausea to participate.
- Not on a pediatric service

The specific criteria for subject selection are patients admitted to Tower 4, an acute care/telemetry unit, who are conscious and able to communicate, that understands the purpose of the study and is competent and can give consent. The patient must not include any of the following:

### Exclusion criteria:

- Cognitively impaired
- Post-op from an otolaryngologic surgery
- Known impaired olfactory function (limited or no sense of smell)
- On any psychiatric holds (e.g., 5150's)
- Known allergies to essential oils.
- Sensitive or allergic to plants (specifically to lavender plants, orange blossoms, sandalwood trees, or peppermint leaves) as essential oils are natural aromas derived from plants.
- Active participant of another Research Protocol
- Admitted as a “short stay” or on “observation” status.
- Has known history of Atrial Fibrillation
- Is a prisoner.
- Known pregnancy, or

## PROTOCOL TITLE: Aromatherapy on Tower 4 (Non-Otolaryngology)

- Expected to be transferred out of Tower 4 and/or discharged from the hospital within 24 hours.

### 5) Study Timelines

Participants of the study will ideally wear the aromatherapy tab on their gown for at least 8 hours to assess its effectiveness. After a minimum of 8 hours has elapsed, they will be given a follow up assessment tool to evaluate their symptoms and their experience in using aromatherapy.

- Identification of eligibility
- Consent
- Assessment 1 (Hour 0)  
Awake - complete assessment tool.
- Aromatherapy tab application
- Assessment 2 (Hour 8)  
Sleeping - no assessment/document sleep  
Awake – complete end assessment tool.  
Satisfaction assessment

If patient prefers, they can continue to utilize aromatherapy, otherwise tab is to be removed, and study is complete.

- Assessment 3 (Hour 12-24)
- Aromatherapy tab removal (after the maximum 24 hours worn)
- Additional data collection as noted below (medication use)

Individual subject participation will total up to 8 hours to a maximum of twenty-four hours.

We anticipate that our goal enrollment of one hundred subjects will be accomplished within six months (from first subject enrolled to last subject). Our total estimate for study completion is twelve months.

### 6) Study Endpoints

**Primary endpoint:** Elequil aromatherapy tab use is effective on

1. Patient-reported pain score
2. Patient-reported anxiety score
3. Patient-reported nausea score

**Secondary endpoints:** Elequil aromatherapy tab use is effective in decreasing the following as measured by the corresponding scales:

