## PROTOCOL TITLE: Aromatherapy on Tower 4 (Non-Otolaryngology)

1. Total anxiolytic medication use
2. Total antiemetic medication use
3. Total opioid medication use
4. Observed and patient-reported sleep.
5. Patient-reported patient satisfaction
6. Patient-reported well-being

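### The secondary objective of improved sleep and well-being has no described starting value, scale or control group to compare against, and Section 6 gives these endpoints the wrong direction

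*Protocol*

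**What the plan says.** Section 2 sets the secondary objective as "improved sleep and improved patient satisfaction and well-being". Its hypothesis adds "increasing sleep and overall patient satisfaction".

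Section 6 introduces the secondary endpoints as outcomes on which the tab is "effective in decreasing the following as measured by the corresponding scales". Six items follow. The first three are total use of anxiolytic, antiemetic and opioid medication. The other three are "Observed and patient-reported sleep", "Patient-reported patient satisfaction" and "Patient-reported well-being".

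On collection:

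- **Baseline.** Section 7 describes a tool on which the subject rates pain, anxiety and/or nausea. The numbered procedure list adds age, gender and unnamed Likert scales.
- **Follow-up.** Item 6 of that list names anxiety, pain and nausea. Section 5 describes a "follow up assessment tool to evaluate their symptoms and their experience in using aromatherapy".
- **Sleep.** At Hour 8 the timeline in Section 5 says "Sleeping - no assessment/document sleep". Item 9d in Section 7 takes insomnia medication from the chart.
- **Satisfaction.** It is assessed at Hour 8 (Section 5) and on an exit survey (Section 7, item 9e).
- **Well-being.** Neither the timeline nor the procedures mention it as an outcome.
- **Scales.** Assessment Tools sets out three, for anxiety, pain and nausea.

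**The concern.** An improvement is a difference from something: the subject's own earlier value or a comparison group. The protocol describes no control group, so the starting value has to carry the comparison. For pain, anxiety and nausea it exists. For sleep and well-being none is described.

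This cannot be left to an analysis plan. Such a plan can define how a change is estimated, but it cannot supply a baseline answer that was never requested, and a baseline cannot be recovered once the tab has been worn. If the forms match the description, the study could report how subjects slept or felt after use. It could not report whether either had improved, which is what two of the three parts of the secondary objective ask.

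The reversed direction in Section 6 is a smaller matter but should not stand, because it contradicts Section 2.

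**Working it through.** No arithmetic beyond counting applies, so the sections are set side by side.

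**Direction**

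| Secondary endpoint | Section 6 | Section 2 |
|---|---|---|
| Three medication totals | decrease | reduced use: agrees |
| Sleep | decrease | improvement (objective), increase (hypothesis): contradicts |
| Satisfaction | decrease | improvement (objective), increase (hypothesis): contradicts |
| Well-being | decrease | improvement (objective only): contradicts |

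Three of six endpoints carry a direction opposite to Section 2.

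**Measurement**

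| Endpoint | In described baseline tool | In follow-up list (item 6) | Scale in Assessment Tools | Other collection described |
|---|---|---|---|---|
| Sleep | no | no | no | Hour 8 note if asleep; insomnia medication from chart |
| Satisfaction | no (none needed) | no | no | Hour 8 assessment; exit survey |
| Well-being | no | no | no | none |

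Of the three scales given, none measures any of these endpoints. Of the two described symptom lists, none names sleep or well-being. Satisfaction is the only one of the three with a named time point for a patient rating.

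**What the Hour 8 sleep note can show**

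1. Assessment 1 requires the subject to be awake to complete the tool, so everyone starts awake. A move from awake to asleep by Hour 8 is partly built into the schedule.
2. The protocol does not fix the time of day at which the tab is applied. A tab applied early in the morning reaches Hour 8 in the afternoon, and one applied in the evening reaches it at night. The share asleep at Hour 8 therefore depends on when tabs were applied, whatever the tab does.
3. A subject asleep at Hour 8 gives no rating then. The content of Assessment 3 (Hour 12-24) is not stated, so it is not known whether a sleep rating is obtained later.
4. Insomnia medication from the chart is related to sleep, but it is neither observed nor patient-reported sleep, and Section 6 does not list it as an endpoint.

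Taken together, the described data give sleep and well-being no before-after contrast. Satisfaction with an intervention needs no baseline. It lacks only a stated scale, and for the same reason it cannot be said to have increased.

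**The case against.** The strongest reply is that the forms themselves are not reproduced. Section 7 says what the baseline tool asks, but not that it asks nothing else. It goes on to speak of assessment tools in the plural, and item 3b lists Likert scales without naming them. The follow-up tool also covers symptoms and experience of use, and Section 12 counts insomnia among the symptoms that might be relieved. Sleep or well-being items may therefore exist. This stands. A reader might infer that sleep and well-being are not measured at all, or that a baseline is certainly absent, and the document does not support either. It supports only that none is described. The baseline gap is the better supported of the two, because Section 7 states that tool's content. An exit question might also record perceived improvement, but only in retrospect.

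Two other strong readings are tempting. One is that the study would count worse sleep or lower satisfaction as success. The text of Section 6 says so literally, but Section 2 makes the intended direction plain, so this is a drafting slip. The other is that Section 6 promises a rating scale for all six endpoints. The first three are medication totals from the chart and have no rating scale, so the phrase is loose drafting and should not be pressed.

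It is also fair to say that only secondary endpoints are affected, and that a before-after change without a control group would be weak evidence even with a baseline. Both limit the weight of the point. Neither removes the need to match the objective to what is collected.

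**Conclusion.** The point holds as a statement about the protocol as described. Section 6 gives 3 of 6 secondary endpoints a direction that contradicts Section 2, which is a wording error. More substantively, sleep and well-being have no described starting value, scale or control group, so improvement in either cannot be estimated from what the protocol sets out. Satisfaction has time points but no scale, and is a post-use rating. The Hour 8 sleep note is not evidence of effect.

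The conclusion assumes that the baseline tool contains what Section 7 says it contains. If the unseen forms already hold identical sleep and well-being ratings before and after use, only the wording needs correcting. Severity is minor to moderate, and the primary endpoints are untouched.

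**What to change.** 1. In Section 6, limit the decrease to the three medication endpoints.
2. For well-being and patient-reported sleep, choose one of two routes:
   - Add one identical short rating for each (for example 0-10, the range already used for pain) at Assessment 1 and at the end assessment. Describe the rating under Assessment Tools, and report the within-subject change with the number of subjects who have both ratings.
   - If no baseline item is collected, restate Sections 2 and 6 so that both outcomes are described after use and not claimed as improved.
3. State satisfaction as a post-use rating with its scale, report it descriptively, and remove the language of improvement or increase for it from Section 2.
4. Record the clock time of the Hour 8 sleeping/awake note and report the note descriptively.

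The cost is one or two extra items on two forms, plus corrected wording in Sections 2 and 6 and the scale entries. The items are worth adding before enrolment, or as early in it as possible. The limitation that remains is that a before-after change without a control group cannot be attributed to the tab alone, and the report should say so.
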